Goldman-Fristoe Test of Articulation. (Goldman-Fristoe, 1986). This test assesses a child's articulation ability by sampling both spontaneous and imitative speech production. Pictures and verbal cues are used to elicit single word answers that demonstrate common speech sounds. The Goldman-Fristoe measures the articulation of speech sounds and identifies and describes the types of articulation errors produced by the child.

Surgery

Nucleus Multichannel ABI will be placed using the retrosigmoid craniotomy on the side opposite the child's previous CI (when present) and assuming there are no obvious contraindications. This approach provides direct access to the lateral recess of the 4th ventricle and region of the cochlear nucleus. This approach has previously been documented to be safe in the literature for this use (48) and has been used extensively in adults and children at our institution for other causes. Our team has extensive experience with cerebellopontine angle surgery (i.e. the region of interest). In 2009-2011, we carried out 71 cerebellopontine angle craniotomies for acoustic neuromas (16 retrosigmoid). In that time period, there were a total of 120 retrosigmoid craniotomies in adults and 42 in children. We have also carried out the only retrosigmoid approach for ABI placement in an adult patient without NFII in the United States to date (see images and description below).

Surgery is carried out under general endotracheal anesthesia, without paralytic agents, and is administered by a pediatric anesthesiologist in a children's hospital operating room. The child

will have 2 large bore intravenous catheters placed. Following induction, the child will be maintained under normotensive anesthesia using a combination of inhalational and intravenous agents. The auditory monitoring montage will be placed as described below. Cranial nerve electromyography monitoring will consist of bipolar, needle electrodes placed in the ipsilateral facial muscles (orbicularis oris and oculi-CN VII), soft palate (CN IX-X), and trapezius (CN XI). Appropriate monopolar needle electrodes will serve as ground and stimulating electrodes and will be placed in the pre-sternal subcutaneous skin. The NIM-Response[®] 3.0 (Medtronic, Minneapolis, MN) nerve integrity monitor will be used to continuously monitor EMG activity under both spontaneous conditions as well as under evoked testing.

The patient will be positioned in an age appropriate head holder in a modified lateral position to expose the suboccipital cranial region. An appropriate location for the receiver stimulator will be identified based on the device templates and marked with injection of methylene blue on to the skull in a routine fashion. A post-auricular incision will be marked and infiltrated with 1 lidcaine and 1:100,000 epinephrine solution. Monopolar cautery will be avoided to protect the child's previous CI. Following skin flap creation, the region of the retrosigmoid craniotomy will be exposed based on standard surgical landmarks (asterion, inion). A standard, retrosigmoid craniotomy (~2.5 x 2.5 cm) will be created, exposed mastoid air cells occluded with bone wax and the suboccipital dura exposed.

Dural incisions will open the posterior cranial fossa and using the operating microscope, CSF is drained from cisterna magna and the lateral cerebellopontine angle cistern with gentle retraction. The posterior-ventral and dorsal cochlear nucleus is the most accessible portion of the nucleus complex for electrical stimulation. These structures are located on the anterior surface of the lateral recess of the 4th ventricle and can be visualized. After cerebellar relaxation, the lower cranial nerves are identified and the IX cranial nerve and choroid plexus emanating from the Foramen of Luschka will be viewed with gentle retraction of the cerebellar flocculus. The facial nerve, ventral to the lateral recess and cochleovestibular nerve and/or its remnant as well as the lower cranial nerves exiting inferiorly are identified and confirmed with stimulation. Opening the recess arachnoid may reveal the choroid plexus and can release CSF to aid in identification. Upon opening the recess, the cochlear nucleus prominence is evident on anterior wall.

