The purpose of this feasibility study is to demonstrate the safety and efficacy of the Nucleus 24 Multichannel Auditory Brainstem Implant (ABI, Cochlear Corp, Sydney, AUS) in children who do not have the diagnosis of neurofibromatosis type II (NFII), and who have either experienced failed cochlear implantation (CI) or have been unable to receive a CI secondary to cochlear or cochlear nerve disorders. These conditions can include: developmental or acquired cochlear nerve deficiency (CND), cochlear aplasia (Michel), post-meningitis cochlear ossification, or cochlear malformation. This study proposes to implant up to 10 pre-linguistic young children (18 mos to 5 yrs. of age) and 5 post-linguistic children (<18 yrs of age) with the Nucleus 24 Multichannel ABI in an attempt to demonstrate safety of the surgical procedure, tolerance of device stimulation, and the potential for auditory benefit beyond that experienced with their CI. This study will provide the preliminary experience for a larger scale clinical trial.

Regulatory Status of the Investigational Device

Data supporting the safety and effectiveness of the Nucleus 24 ABI were provided to the United States Food and Drug Administration (FDA) in March 2000, as part of a Premarket Approval Application. On July 21, 2000, the Agency's Ear, Nose and Throat (ENT) Advisory Panel unanimously recommended that FDA release the Nucleus 24 ABI for use by individuals with NFII above the age of 11 years. Cochlear Americas received a letter of approval from the Agency in October 2000 (PMA No P000015). The letter is enclosed.

The Nucleus 24 ABI features a multichannel electrode lead that terminates in twenty-one, 0.7 mm platinum disk-electrodes. The 21 platinum contacts are arranged on the surface of a silicone rubber pad in three rows of seven contacts and are surgically placed on the surface of the brainstem; specifically, on the surface of the cochlear nucleus.

Background and Rationale

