The only absolute contraindication to CI is an absent cochlea or an absent cochlear nerve. In addition, patients at risk for lower levels of performance include those with anatomic conditions that adversely affect the electrode-neural interface such as developmental labyrinthine malformations and cochlear ossification and fibrosis secondary to meningitis. While the diagnosis of cochlear (i.e. Michel) aplasia is clear clinically, the diagnosis of cochlear nerve aplasia is made somewhat more challenging by the spatial resolution of current imaging modalities (26-29). Because of this uncertainty, the term cochlear nerve deficiency (CND) was coined to refer to the situation where the cochlear nerve is small or absent on high resolution magnetic resonance imaging (MRI), or where the bony cochlear nerve aperture and canal are small or absent on temporal bone computed tomography (CT). The clinical diagnosis of CND includes these imaging findings in the setting of profound hearing loss (29, 30). Auditory brainstem response testing that shows a present cochlear microphonic but absent neural waves can support the diagnosis (29).

In an effort to provide hearing to deaf children who have inner ear malformations, CND, or ossification from meningitis, CI has been undertaken over the years (30). This might be considered the standard of care today for those who desire spoken language communication. Results of these interventions suggest that most children with CND gain some sound awareness from these devices using higher levels of electrical stimulation. However, achievement of open set speech perception for the purposes of speech and language development has been largely unsuccessful, probably as a result of a poor electrode-neural interface and other associated conditions (30-33). In the study from our institution, only 19% of children with CND developed any open set speech perception using their CI, and none of these children were able to communicate using auditory-only information (i.e. all used some supplemental sign language).

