This study is an early feasibility study of the Nucleus 24 ABI in children without NFII. It will be conducted as a repeated-measures, single subject experiment with up to 10 replications (i.e. 10 total subjects). A single-subject research design was chosen (in which each subject serves as their own control) in order to accommodate the heterogeneity that is well known to characterize auditory prosthesis research. Post-operative evaluations will be conducted at the initial activation and at 1, 3, 6, 12, 18, 24, 30, and 36-month intervals post-activation. A 36-month follow-up was chosen in an effort to demonstrate the emergence of open-set speech perception abilities prior to study cessation. Experience in the CI literature has shown that a minimum of 2 years of device usage is required for children with pre-lingual hearing impairment to develop some open-set speech perception abilities (50). Blinding or masking procedures are not included in the design, as the presence/absence of a brainstem implant cannot be easily concealed from the device recipients and/or clinical investigators.

Preoperative measures will include high-resolution brain MRI, temporal bone CT and standardized, developmentally appropriate audiological and speech and language development test batteries. Children between 18 mo and 5 yrs of age with one of the anatomic conditions mentioned below and a present and patent cochlea will have previously received a CI as a precondition prior to consideration and will have demonstrated very limited to no benefit from

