- Pre-linguistic hearing loss (birth-5 yrs.; age at ABI 18 months-5yrs) with both:
 - MRI +/- CT evidence of one of the following:
 - Cochlear nerve deficiency
 - Cochlear aplasia or severe hypoplasia
 - Severe inner ear malformation
 - Post-meningitis ossification
 - When a cochlea is present or patent, lack of significant benefit from CI despite consistent use (≥ 6 mo.)
 - No or limited speech perception ability (limited to pattern perception on closed set testing materials using the CI)

- Lack of progress in auditory skills development

18 months of age was chosen for the lower age limit to minimize the adverse effects of auditory deprivation on speech perception, speech production, and language development (23, 50). Moreover, 18 months of age will allow for a child to receive a CI at 1 year of age and have at least 6 months of device experience prior to considering ABI. Six months of CI usage prior to ABI consideration was chosen as this time period to allow for clear demonstration of lack of benefit as defined as either: (1) lack of sound awareness, or (2) where elevated charge requirements, absent ECAPs, elevated pure tone averages (>45 dB), and no or limited speech perception abilities are evident. To determine if a child is making significant progress both subjective and objective measures are used. Objectively, standardized speech perception, production, and language tests (as described below) are administered to determine if standard scores are following typical developmental patterns, even at a reduced rate. No or limited speech perception abilities will be considered when there are no improvement in IT-MAIS, or ESP measures from preop measures at the 6 month post-CI interval (30, 50). Developmental norms are also determined based on the hearing age. For example, a child who is 9 months old receptively understands between 3 and 50 vocabulary words and approximately 300 between the ages of 2 and 3. Does the child with a hearing age of 9 months understand this many words? For early speech development, all English vowels should be present by a hearing age of 12 months. Children 18 months of age can be tested using the standardized measures to determine progress.

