Patients will come from either the UNC Ear and Hearing and pediatric CI practices (>100 new patients/yr.) or from outside the institution. It is anticipated that potential subjects from outside the institution will hear about the study through discussion among colleagues. The records of the UNC children currently in our program and known to have cochlear or cochlear nerve disorders that would make them potential candidates will be reviewed by the principal investigator to identify their potential candidacy. Children with such disorders are currently tracked as a part of the principal investigator's secure patient list in WebCIS (Inner ear malformations list). During a routine patient visit, general interest in the study will be discussed in privacy. Should there be general interest, a detailed (~1 hr.) discussion will be scheduled to go through the entire protocol and consider informed consent. Both subjects that are interested and those uninterested in participation will be tracked and recorded. For those subjects that are not patients of the principal investigator, a knowledgeable individual will provide the subject with information and contact details of the investigator. The prospective subject can then initiate contact, if desired. There are no criteria that limit access among women or minorities. The requirement for participants to be primary English speaking families will limit access among non-English speaking individuals. This is a precondition because the investigators must be able to administer and judge speech and language test results that are English only in nature. This also allows for analysis among similar types of tests materials. Given the small number of participants, this is an unavoidable precondition.

The Principal Investigator will inform the parent or guardian about all aspects of the study for implantation of the Nucleus 24 ABI including: study expectations and requirements, surgical procedure, and the postoperative evaluations and schedule. The risks of surgery and activation will be explained to the parent or guardian as outlined in the Institutional Review Board (IRB)-approved Informed Consent Form. The potential limitations and advantages of implantation with the Nucleus 24 ABI shall also be explained.

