A single-subject research design was chosen (in which each subject serves as their own control) in order to accommodate for the heterogeneity that is well known to characterize auditory prosthesis research. Post-operative evaluations will be conducted at the initial activation and at 1, 3, 6, 12, 18, 24, 30, and 36-month intervals post-activation. Blinding or masking procedures are not included in the design, as the presence/absence of a brainstem implant cannot be easily concealed from the device recipients and/or clinical investigators.

Data will include demographics, frequency of both major and minor complications as well as audiometric and speech and language data. The summary statistics will be reported on the various categorical (gender and complications) and continuous (age, audiological and speech perception, production and language scores) variables.

Baseline audiological and speech perception, production and language measures taken prior to ABI surgery will be compared to scores at each follow up interval within each subject. For subjects with no response on behavioral testing, a maximum score of 120 dB HL will be assigned at the test frequency as this represents maximum stimulus levels of the equipment. Pure tone average (PTA) is calculated using the thresholds from 500, 1,000, and 2,000 Hz. When speech perception testing is limited by short duration experience or young age, inattention, or the presence of significant comorbidities, these reasons will be recorded. When inability to complete the test is evident despite significant implant experience, the patient is assigned the value for chance correct responses for the appropriate test (i.e., 0% for open-set tests or 33% for ESP pattern-[P] perception tests). When a child advances out of a particular measure because of ceiling effects, then the next measure will be undertaken. For children able to perform a given speech perception measure(s) prior to ABI surgery, that measure(s) will be repeated at the initial post-operative visits to insure the same test comparisons exist. It will be assumed that children that are unable to perform closed set testing will not be able to perform open set testing at a given visit. Thus, scores on these tests will be assigned the value of “unable to test”.

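### For pre-linguistic children with short prior CI use, a late open-set gain over baseline cannot by itself show that the ABI does better than the CI

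*Combined protocol and SAP*

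**What the plan says.** **The comparison wanted.** The opening statement of purpose includes "the potential for auditory benefit beyond that experienced with their CI". Specific Aims 2 and 3 are narrower and refer only to each child's own starting point.

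**Time needed for open-set perception.** The Protocol section states: "a minimum of 2 years of device usage is required for children with pre-lingual hearing impairment to develop some open-set speech perception abilities". It gives the emergence of this skill as the reason for three years of follow-up, with evaluations "at the initial activation and at 1, 3, 6, 12, 18, 24, 30, and 36-month intervals post-activation". Study Endpoints treats absence of open-set perception only at three years as good evidence of no benefit on that measure.

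**CI use before the ABI.** Under Inclusion Criteria, a pre-linguistic child with a present or patent cochlea needs at least 6 months of consistent CI use: "Six months of CI usage prior to ABI consideration was chosen as this time period to allow for clear demonstration of lack of benefit". Failure is then defined in one of two ways. One is no sound awareness. The other is a combination of high charge needs, absent ECAPs, pure tone averages above 45 dB and poor speech perception, the last read as no improvement on IT-MAIS or ESP.

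**The analysis.** In Data and Analysis, "Baseline audiological and speech perception, production and language measures taken prior to ABI surgery will be compared to scores at each follow up interval". This is done separately for every child, with significance judged by 95% confidence intervals where possible. The same section later reasons that, because the children are deaf, any meaningful open-set perception, or closed-set perception past patterns, is due to the device.

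**What a CI alone can do.** Background and Rationale reports from the same institution that "only 19% of children with CND developed any open set speech perception using their CI" (CND is cochlear nerve deficiency).

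**The concern.** The plan runs two clocks. The ABI is given 36 months because open-set perception is slow to emerge. The CI score that serves as baseline may be taken at 6 months, when by the plan's own figure open-set perception is not yet to be expected. At that baseline the open-set score is at floor whether or not the CI would eventually have delivered some open-set perception.

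A rise from that floor at month 24 or later shows that the child now hears well enough to recognise words. It does not show that the child would not have done so on the CI. The attribution sentence treats the counterfactual as zero, although the plan's own background figure for CND is not zero.

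The study is meant to prepare a larger trial. One or two late open-set achievers, read as benefit over the CI, would carry an untested comparison into that trial's rationale.

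**Working it through.** **1. Plan's own figure.** The documents give no sample size, power or expected count for ABI against CI, so there is nothing to reproduce on that contrast. The age limit in Inclusion Criteria agrees with its inputs: CI at 12 months + 6 months of use = 18 months.

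**2. Exposure at the minimum of 6 months.** Shortfall against the plan's 2 years: 24 − 6 = 18 months. Ratio of ABI to CI use = visit month / 6:

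| ABI visit (months) | 6 | 12 | 18 | 24 | 30 | 36 |
|---|---|---|---|---|---|---|
| Ratio | 1 | 2 | 3 | 4 | 5 | 6 |

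The visits at which open-set perception is expected (24 to 36) carry four to six times the baseline CI exposure. The one matched visit, month 6, lies before the 2-year mark for both devices, so it is floor against floor for open-set scores. It is informative only for early markers.

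**3. Open-set achievers expected without an ABI.** Let n be the number of children with a prior CI and p the chance of reaching open-set perception on continued CI. Then P(at least one) = 1 − (1 − p)^n. Inputs:

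- n = 10: the enrolment cap in Methods and Subjects, and an upper limit here, because children without a usable cochlea need no prior CI.
- n = 5: an assumption.
- p = 19%: the plan's figure for children with CND generally. Children selected for no progress at 6 months should do worse, so it is an upper guide.
- p = 2%, 5%, 10%: assumptions, since the documents give no rate for that selected group.

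| p | n = 10, at least one | n = 10, at least two | n = 5, at least one |
|---|---|---|---|
| 2% | 18% | 2% | 10% |
| 5% | 40% | 9% | 23% |
| 10% | 65% | 26% | 41% |
| 19% | 88% | 59% | 65% |

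Example: 1 − 0.95^10 = 1 − 0.599 = 0.401. At 19% the expected number among ten is 10 × 0.19 = 1.9.

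**4. How many achievers would stand out.** Illustration with n = 10 and one-sided 5%. Against 19%, four or more has probability 0.104 and five or more 0.027, so five would be needed. Against 10%, three or more has 0.070 and four or more 0.013, so four would be needed. At these rates one or two would not suffice.

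**5. Are the plan's safeguards tied to the claim?** Data and Analysis stacks the speech tests into one index (SRI-Q), plots it over time against CI children with and without malformations, and says the results allow for length of device use and age at implantation. It gives no method for that allowance. Neither the baseline comparison nor the attribution sentence refers to the display.

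**The case against.** The strongest defence has four parts.

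*The 6-month decision does not rest on open-set scores.* The Protocol section mentions lack of open-set perception as one sign of poor CI benefit. The operative rule in Inclusion Criteria uses sound awareness, charge, ECAPs, thresholds, IT-MAIS and ESP. Exclusion Criteria adds that nearly all children with a good CI signal are at IT-MAIS ceiling and above chance on ESP patterns by then. This stands. A reader might infer that the plan declares CI failure merely because open-set perception is missing at 6 months; the documents do not say that. The rule lowers the counterfactual rate but does not make it zero, and the plan gives no rate for children so selected.

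*Duration is not ignored.* A reader might infer that the devices are never compared at equal use, or that the outside curves describe CI children in general. Neither is right. The SRI-Q display is by time, its comparators include CI children with malformations, and the cited cohort from the same institution covers labyrinthine anomalies and CND. Language results are also read against hearing age with the ABI. The contralateral ear is chosen partly so that performance can be compared during follow-up. What remains is that these elements are descriptive and have no stated method. The test list names individual ears only for the detection audiogram.

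*The claim is modest.* Aims 2 and 3 concern change from baseline, and Data and Analysis expects only some idea of efficacy before a larger trial. This stands for hearing provided by the ABI. It does not cover the purpose statement, which names benefit over the CI.

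*Not every child is affected.* Children without a usable cochlea have no CI baseline. Post-linguistic children must already have had open-set perception, so the emergence argument touches them less. Some pre-linguistic entrants may have used a CI well beyond 6 months. All of this stands and limits the scope.

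**Conclusion.** The point holds for pre-linguistic children with a prior CI, above all those near the 6-month minimum. For them, the baseline contrast sets up to 36 months of ABI use against a CI score taken before the plan's own 2-year mark. A late open-set gain over that baseline does not, alone, establish benefit over the CI. The existing safeguards reduce the problem, but the plan does not connect them to the significance comparison or the attribution.

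The size depends on two unknowns: how many children have a prior CI, and their open-set rate on continued CI. Over the ranges in the table, the chance of at least one such achiever without an ABI runs from 10% (five children, 2%) to 88% (ten children, 19%). The upper end assumes that all ten had a prior CI and that selection for no progress at 6 months makes no difference. It is a bound, not an estimate.

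A reader might go further and infer that any benefit seen would be an artefact of longer exposure. The documents do not support that. Early-marker gains are less affected, and gains over baseline still bear on whether the ABI provides hearing.

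**What to change.** Changes to Data and Analysis and to reporting; eligibility, treatment and visits stay as they are.

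1. Report each child's duration of CI use at baseline.
2. Use the month 6 ABI-versus-CI contrast for early markers only (IT-MAIS, ESP, thresholds).
3. Base any statement of benefit over the CI at months 24 to 36 on a comparison with the institution's existing CI children with CND or malformations, already cited for the SRI-Q display, at the same duration of use. Where data allow, restrict that cohort to children with no progress at 6 months who stayed on the CI. State how duration and age at implantation are handled.
4. Reword the attribution sentence. Gains over baseline show that the ABI provides hearing; superiority to continued CI is claimed only for gains exceeding that comparator.

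Testing families who decline is not part of this request. Under Screening, Informed Consent, and Enrollment, "Both subjects that are interested and those uninterested in participation will be tracked and recorded", but that passage concerns recruitment and mentions no outcome testing, which would need extra resources.

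The cost is revised analysis text and re-extraction of existing clinic data. The restricted cohort's size is unknown and may be small, so the benefit claim becomes more modest and less precise.
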